## **5. TREATMENT OF SUBJECTS**

NA. Observational cross-sectional study.

### **5.1. Investigational product/treatment**

NA

### **5.2. Use of co-intervention (if applicable)**

NA

### **5.3. Escape medication (if applicable)**

NA

**6. INVESTIGATIONAL PRODUCT**

NA. Observational cross-sectional study.

**6.1. Name and description of investigational product(s)**

NA

**6.2. Summary of findings from non-clinical studies**

NA

**6.3. Summary of findings from clinical studies**

NA

**6.4. Summary of known and potential risks and benefits**

NA

**6.5. Description and justification of route of administration and dosage**

NA

**6.6. Dosages, dosage modifications and method of administration**

NA

**6.7. Preparation and labelling of Investigational Medicinal Product**

NA

**6.8. Drug accountability**

NA

**7. NON-INVESTIGATIONAL PRODUCT**

NA. Observational cross-sectional study.

**7.1. Name and description of non-investigational product(s)**

NA

**7.2. Summary of findings from non-clinical studies**

NA

**7.3. Summary of findings from clinical studies**

NA

**7.4. Summary of known and potential risks and benefits**

NA

**7.5. Description and justification of route of administration and dosage**

NA

**7.6. Dosages, dosage modifications and method of administration**

NA

**7.7. Preparation and labelling of Non Investigational Medicinal Product**

NA

**7.8. Drug accountability**

NA

## 8. METHODS

### 8.1. Study parameters/endpoints

#### 8.1.1. Main study parameter/endpoint

Glycemic control assessed by HbA1c (mmol/mol)

#### 8.1.2. Secondary study parameters/endpoints (if applicable)

- Glucose variability assessed by the standard deviation (SD) of glucose values during continuous or flash glucose monitoring
- Extent of well-being as assessed by the WHO-5
- Extent of psychological distress as assessed by the 'Perceived Stress Scale'(PSS) and 'Problem Areas in Diabetes'(PAID)
- Evaluation of self-management behaviour measured by 'Summary of Diabetes Self-Care Activities'(SDSCA) and 'Diabetes Self-Management Questionnaire' (DSMQ-R)

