The current study aims to assess the impact of self-quarantine on glycemetic control in patients with type 1 and type 2 diabetes. In addition, this study describes diabetes self-management, well-being and distress in Dutch patients with type 1 and type 2 diabetes, during a nationwide period of self-quarantine.

It is hypothesized that experiencing this period of nationwide quarantine influences glycemetic control and that patients reporting severe distress or low well-being experience more

problems in regard to diabetes self-management and maintaining glyceimic control than those without psychological distress or low well-being (13).

Research hypotheses:

H1: Experiencing self-quarantine impacts glyceimic control and glucose variability

H2: a) Experiencing high levels of distress is related to (poorer) glyceimic control

H2: b) Experiencing low levels of well-being is related to (poorer) glyceimic control

H3: a) Experiencing high levels of distress is related to suboptimal diabetes self-management

H3: b) Experiencing low levels of well-being is related to suboptimal diabetes self-management

H4: Experiencing self-quarantine impacts HbA1c, glucose variability, well-being, distress and self-management more in patients with type 1 than in patients with type 2 diabetes

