### Secondary Objective(s):

- To determine the effect of a period of nationwide self-quarantine on glucose variability assessed by the standard deviation (SD) of glucose values (glucose variability) in patients with type 1 and type 2 diabetes
- To assess the association between well-being and glycemc control during a period of nationwide self-quarantine. Well-being will be measured by the WHO-5.
- To assess the association between (diabetes) distress and glycemc control during a period of nationwide self-quarantine. (Diabetes) distress will be measured by 'Perceived Stress Scale'(PSS) and 'Problem Areas in Diabetes' (PAID).
- To assess the association between diabetes self-management and glycemc during a period of nationwide self-quarantine. Self-management behaviour will be measured by the 'Summary of Diabetes Self-Care Activities' (SDSCA) and 'Diabetes Self-Management Questionnaire-rev.' (DSMQ-R)
- To determine differences HbA1c, glucose variability, well-being, distress and self-management between patients with type 1 and type 2 diabetes

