## 10. STATISTICAL ANALYSIS

- Categorical data: gender, level of education, type of diabetes, medication use, type of blood glucose measurements (fingerprick or glucose sensor (FGM/CGM)) will be presented by percentage and standard deviation (SD).
- Continuous variables: age, BMI, weight, height, HbA1c will be presented using the mean and the standard deviation (SD). Derived parameters: BMI will be calculated from height (m) and weight (kg) using the formula  $(\text{weight (kg)} / (\text{height (m)})^2)$  and will be presented as continuous variable by mean and standard deviation (SD). Glucose variability will be calculated by the standard deviation of the glucose values from the continuous and flash glucose monitors obtained during the previous week in the quarantine period. This SD will be compared to the SD from the glucose values during the last non-quarantine week. Other glyceic measures include time spent in range 4.0-10.0 mmol/l, time spent in hypoglycaemia (<3.0, 3.0-3,5, and 3.5-3.9 mmol/l), time spent in hyperglycemia ( $\geq 10.0$  mmol/l)
- Missing data will be excluded from analyses.

- Data will be statistically analysed using STATA intercooled 16.0. HbA1c measurements and SD measurements prior to and after the quarantine period will be compared using a paired-sample t-test in case of normal distribution or Wilcoxon Signed Rank Test in case of abnormal distribution. Furthermore, differences in HbA1c and glucose variability between patients with type 1 and type 2 diabetes will be measured using independent T-tests. Differences in well-being, distress and self-management between patients with type 1 and type 2 diabetes will be analysed using independent T-tests. The association between glucose variability and parameters for distress, well-being and self-management will be analysed using multivariate regression analysis.

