### 10.2. Secondary study parameter(s)

#### **Standard deviation (SD) of glucose values**

In patients who wear a continuous or flash glucose sensor the SD of the glucose values will be determined in the previous week before uploading the glucose data during the quarantine period. The SD will be compared to the SD during the last non-quarantine week.

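### Glucose variability is measured only by the raw SD, so a change in mean glucose can show up as a change in variability and the planned analyses cannot tell the two apart

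*Protocol*

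**What the plan says.** The choice of metric is fixed consistently across the protocol. The first secondary objective in section 2 concerns "glucose variability assessed by the standard deviation (SD) of glucose values (glucose variability) in patients with type 1 and type 2 diabetes". Section 8.1.2 repeats it as an endpoint: "Glucose variability assessed by the standard deviation (SD) of glucose values during continuous or flash glucose monitoring". Section 10 gives the derivation: "Glucose variability will be calculated by the standard deviation of the glucose values from the continuous and flash glucose monitors", using one week within quarantine. Section 10.2 sets the reference period: "The SD will be compared to the SD during the last non-quarantine week".

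Three analyses use this SD, all in section 10:

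- **Within patient.** The before and during values "will be compared using a paired-sample t-test in case of normal distribution or Wilcoxon Signed Rank Test in case of abnormal distribution".
- **Between diabetes types.** "differences in HbA1c and glucose variability between patients with type 1 and type 2 diabetes will be measured using independent T-tests".
- **Regression.** "The association between glucose variability and parameters for distress, well-being and self-management will be analysed using multivariate regression analysis".

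Section 10 also lists other sensor measures: time in range, and time in bands of low and high glucose. Mean glucose and CV are not among them. On the hypothesis side, section 1 states "H1: Experiencing self-quarantine impacts glyceimic control and glucose variability", and its background text expects anxiety or distress to push glucose upward.

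**The concern.** H1 names glycaemic control and glucose variability side by side, so readers will take a significant change in SD as evidence about stability in addition to level. The SD does not guarantee that. If every reading rises by the same proportion, the SD rises by that proportion while relative variability stays put. The study is built on the expectation that the level moves, so this is a likely setting.

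The same ambiguity affects the other two uses. If type 1 and type 2 patients differ in mean glucose, their SDs can differ for that reason alone. If distress goes with higher glucose, as H2 proposes, an association between SD and distress may only repeat the association with level. In the other direction, a fall in the mean could mask an increase in relative swings. At stake is the interpretation of a named secondary objective and of the variability parts of H1 and H4. The primary HbA1c analysis is not affected.

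**Working it through.** **The plan's own figures.** The protocol gives no mean glucose, CV, effect size or number of sensor users for this endpoint. Its only sample-size figure is for HbA1c (section 4.4). It reproduces as a two-sided comparison of two independent means: 2 × (11 × (1.960 + 1.282) / 4)² = 158.9, so 159 per group. Invitations are 159 / 0.35 / 0.80 = 567.9, so 568 per group and 1136 in total. These figures do not bear on the present point.

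**Inputs, all assumed for illustration.** Mean glucose 9.0 mmol/l; CV 36%, so SD = 0.36 × 9.0 = 3.24 mmol/l; rise in mean 0.5 mmol/l.

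**Step 1: two kinds of shift.**

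| Shift | New mean | New SD | Change in SD | New CV |
|---|---|---|---|---|
| Additive (+0.5 to each reading) | 9.5 | 3.24 | 0% | 3.24 / 9.5 = 34.1% |
| Proportional (each reading × 9.5 / 9.0) | 9.5 | 0.36 × 9.5 = 3.42 | 0.18 / 3.24 = +5.6% | 36% |

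The SD is blind to the additive shift and moves with the proportional one. The CV does the reverse.

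**Step 2: range under the proportional case.** The SD changes by CV × rise, and its relative change is rise / mean. For CVs of 30–42%, means of 8–10 mmol/l and rises of 0.25–1.0 mmol/l, the SD changes by 0.30 × 0.25 = 0.075 up to 0.42 × 1.0 = 0.42 mmol/l. In relative terms this is 0.25 / 10 = 2.5% up to 1.0 / 8 = 12.5%. Under the additive case every one of these changes is zero.

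**Step 3: would a test detect it?** Take the proportional 0.5 mmol/l rise, so the SD changes by 0.18 mmol/l with CV constant. With n sensor users and s the between-patient standard deviation of the change in SD, the rejection probability of a two-sided 5% paired test is approximately Φ(0.18√n / s − 1.96) + Φ(−0.18√n / s − 1.96). Both n and s are assumed.

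| n | s = 0.4 | s = 0.6 | s = 0.8 |
|---|---|---|---|
| 40 | 0.81 | 0.48 | 0.30 |
| 80 | 0.98 | 0.77 | 0.52 |
| 159 | 1.00 | 0.97 | 0.81 |

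Under the additive shift the probability stays at 0.05 throughout.

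**Step 4: between types.** At a common CV of 36%, group means of 9.0 and 10.0 mmol/l give SDs of 3.24 and 3.60. That is a difference of 0.36 / 3.24 = 11.1% with equal relative variability.

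**Step 5: do the listed sensor measures resolve it?** In a lognormal simulation with the same assumed mean and CV, time at or above 10 mmol/l rose from 31.7% to 37.1% (additive) or 37.4% (proportional). Time in range fell from 66.7% to 62.3% or 61.5%. These measures reveal that the level moved, but scarcely distinguish the two kinds of shift.

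**The case against.** The opposing case is substantial. The protocol defines variability as the SD everywhere, without contradiction, and comparing SDs answers the objective as section 2 words it. Absolute variability is a legitimate target, and nothing in the protocol says relative variability was intended. H1 does not claim that level and variability are independent. The proportional figures follow from assuming a constant CV, and the lower end of the range is zero. All of this stands.

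It also rules out stronger readings that a reader might infer: that any shift in average glucose will necessarily appear as a change in SD, that the SD is not a separate outcome, that the objective cannot be answered, or that CV should take the SD's place. The protocol contains no data on how spread relates to mean glucose. CV has the mirror-image weakness, falling from 36% to 34.1% in the example although the absolute swings are unchanged.

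Two further arguments carry less weight. The first is that HbA1c and the time-in-range measures show the level. They would reveal a shift, but the time-in-range measures do not separate its kinds. The earlier HbA1c may also date from 6 or 12 months before quarantine (sections 8.3 and 3 differ), so it does not describe the sensor weeks. The second is that a separate statistical analysis plan could add the missing measures. It could, and the protocol lists no adjustment covariates for the variability regression, so their absence there is not in itself a fault. But the protocol does fix the metric and names its companion sensor measures, without including one that speaks to this question.

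**Conclusion.** The point holds as a limit on interpretation. The SD is the only variability measure, the level is expected to change, and the planned outputs cannot show whether a change in SD reflects higher glucose, relatively less stable glucose, or both. For a 0.5 mmol/l rise, the part of the SD change attributable to level is 0% if the shift is additive and +5.6% if proportional, at an assumed mean of 9.0 mmol/l and CV of 36%. A mixture of the two would fall in between. Whether such a change reaches significance depends on the number of sensor users and the spread of the change in SD, neither of which the protocol gives. The SD remains valid for absolute variability. The matter concerns a secondary endpoint in the subset wearing sensors and is worth correcting before analysis.

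**What to change.** In sections 8.1.2, 10 and 10.2:

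1. Keep the SD as the specified variability measure.
2. Compute mean glucose and CV (SD divided by mean) from the same quarantine week and the same final pre-quarantine week.
3. Run the same paired and type 1 versus type 2 comparisons on both.
4. In the variability regression, include mean glucose as a covariate, or repeat the model with CV as the outcome.
5. State in advance that a change will be described as greater instability only when SD, CV and mean glucose have been read together.

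The cost is wording in three sections and one or two extra sensor measures to report. All come from the download already planned. CV has its own dependence on the mean, so it should stand beside the SD and not displace it.

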#### 8.1.3. Other study parameters (if applicable)

Baseline characteristics: age, gender, length, weight, type of diabetes, level of education, medication use, social situation, employment, impact of self-quarantine on daily routines, and health status.

### 8.2. Randomisation, blinding and treatment allocation

NA

### 8.3. Study procedures

Eligible patients from the diabetes outpatient clinic will be sent a letter with study information and informed consent forms. Within several days after receiving the letter, patients will be contacted by phone and will be invited to participate in the study as well as given the opportunity to ask questions. If patients are willing to participate they will be asked to sign the informed consent form and send it back to the LUMC by mail. Once informed consent is provided, patients will be sent a HbA1c fingerprick measurement envelope. They will be asked to fill the tube with several drops of blood up to a mark on the tube and send the envelope back to the LUMC postage free. At the LUMC the HbA1c will be measured by the clinical chemistry lab.

If patients are using a continuous or flash glucose monitoring device data of the most recent 3 months will be collected according to standard clinical practice.

Additionally, patients will receive a link in their e-mail to a set of online questionnaires, containing the DSMQ-R, SDSCA, PSS, PAID and WHO-5, along with questions about level of education, medication use, social situation, employment, impact of self-

quarantine on daily routines, and health status.

The HbA1c measurement and questionnaire will be performed once two months after the start of the nationwide quarantine phase as a result of the COVID-19 outbreak.

Data on HbA1c measurements in the 6 months prior to the period of nationwide self-quarantine will be retrieved from the electronic health record of each patient.

#### **8.4. Withdrawal of individual subjects**

Subjects can leave the study at any time for any reason if they wish to do so without any consequences. The investigator can decide to withdraw a subject from the study for urgent medical reasons.

##### **8.4.1. Specific criteria for withdrawal (if applicable)**

- Patient tested COVID-19 positive within 2 weeks after the HbA1c measurement
- Patient diagnosed with a malignancy, potentially resulting in unreliable HbA1c values
- Patient pregnant during HbA1c measurement in retrospect

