### 3. STUDY DESIGN

This study is an observational, cross sectional study to assess the impact of self-quarantining on glyceimic control, diabetes self-management, distress and well-being. Patients with type 1 and type 2 diabetes mellitus currently in care at the diabetes outpatient clinic of the LUMC will be eligible to participate and will receive information about this study and an informed consent form. A few days later they will be contacted by phone to resolve any questions they may have and ask if the patient wants to participate in the study. If patients want to participate, they will sign the informed consent form and send it to the LUMC by mail. Once informed consent is provided, patients will be sent an envelope including a fingerprick device and a small tube. They will be asked to fill the tube with several drops of blood up to a mark on the tube and send the envelope back to the LUMC postage free. At the LUMC the HbA1c will be measured by the clinical chemistry lab. If the patients wears a continuous or FSL sensor, sensor data will be collected according to standard clinical practice. Furthermore, patients will receive a link by e-mail to a set of online questionnaires, containing the DSMQ-R, SDSCA, PSS, PAID and WHO-5, along with questions about level of education, medication use, employment, social situation and the impact of self-quarantine on daily routines. The HbA1c measurement and questionnaire will be performed at least 6 weeks after starting the quarantine period but still within a period of quarantine measures. Questionnaires will assess the extent and impact of the quarantine measures for each individual patient and assess the effect on glyceimic control, distress and well-being. Data on HbA1c measurements in the 12 months prior to the period of nationwide self-quarantine will be retrieved from the electronic health record of each patient, if available.

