### 4.2. Inclusion criteria

In order to be eligible to participate in this study, a subject must meet all of the following criteria:

- Age  $\geq$  18 years
- Diagnosed with type 1 or type 2 diabetes
- Ability to perform fingerpricks
- Sufficient comprehension of the Dutch language
- Ability to fill out online questionnaires

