### 4.3. Exclusion criteria

A potential subject who meets the following criterium will be excluded from participation in this study:

- Pregnancy
- Newly diagnosed malignancy, with the exclusion of non-melanoma skin cancer, in the previous 6 months
- Chemotherapy or immunotherapy for malignancy
- Admission to hospital or rehabilitation center

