### 4.4. Sample size calculation

Patients with type 1 and type 2 diabetes mellitus are eligible for participation. HbA1c is the primary outcome parameter. Blood for HbA1c will be collected at home by a fingerprick and send to the LUMC. This is a method to obtain insight in glycemc control that many patients perform, and prefer, in clinical practice as it saves them a visit to the hospital. The clinical laboratory in the LUMC is set up to analyse these samples. But this method, which is appropriate in the context of social distancing and limiting hospital visits during this COVID-19 outbreak, also has some consequences regarding the number of patients that need to be approached. From clinical practice we know that not all patients carry out the blood sampling in an appropriate way, despite clear instructions. Also the duration in the postal service renders some samples not suitable for analysis. In this COVID-19 period the postal service

may take longer than normal. Based on our experience from clinical practice and the current COVID-19 situation we estimate that 20% of samples cannot be analysed for HbA1c. The aim is to detect a difference in HbA1c of 4.0 mmol/mol (standard deviation 11 mmol/mol) in comparison to the HbA1c prior to the period of quarantine, which is considered to be clinically relevant in our population of patients with often well regulated diabetes. For an alpha error of 0.05 and a power of 90%, the minimum sample needed is 159 patients per patient group (type 1 and type 2 diabetes). Taking in consideration an estimated response rate of 35% and an estimated proportion of 20% of HbA1c missing measurements as a result of logistical, practical or technical problems, 568 patients per patient group (type 1 and type 2 diabetes) will be invited to participate. This is a total of 1136 patients. The numbers of participants mentioned above are much higher than the number that is minimally needed (15 per variable) to calculate the hierarchical regression analyses (see statistical analyses) on secondary outcomes.

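### The primary HbA1c pair takes the last pre-quarantine value whatever the patient's state at that time, so a change after a recent diagnosis or an ended pregnancy counts as a quarantine effect

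*Protocol*

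**What the plan says.** Protocol 10.1 sets the fingerprick HbA1c against the latest value from before quarantine. Section 10 tests the difference with a paired t-test, or a Wilcoxon signed rank test if the data are not normal, and adjusts for nothing.

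The only condition on the prior value is its age. Section 3 has "Data on HbA1c measurements in the 12 months prior to the period of nationwide self-quarantine will be retrieved from the electronic health record"; section 8.3 gives 6 months; the Summary asks for the most recent value.

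The rules on the patient's state are these:

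- Inclusion (4.2): "Diagnosed with type 1 or type 2 diabetes", with no minimum time since diagnosis.
- Exclusion (4.3): pregnancy, undated; a new malignancy within the preceding 6 months; chemotherapy or immunotherapy for malignancy, undated; and "Admission to hospital or rehabilitation center", undated.
- Withdrawal (8.4.1): a malignancy diagnosis that may make HbA1c unreliable, undated; and "Patient pregnant during HbA1c measurement in retrospect".

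The data listed in 8.1.3 begin "Baseline characteristics: age, gender, length, weight, type of diabetes, level of education, medication use" and go on to social situation, employment, impact on routines and health status. Neither date of diagnosis nor diabetes duration appears there, in section 10, or in the record extraction described in the Summary.

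**The concern.** The primary result is a within-patient difference, so the prior value matters as much as the study value. Section 8.4.1 accepts that pregnancy and malignancy can spoil an HbA1c, but does not clearly carry that principle to the earlier half of the pair.

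Two kinds of patient pass through the rules as written. The first was diagnosed shortly before quarantine and has no later pre-quarantine value, so the value at diagnosis becomes the baseline. The second was pregnant at her last prior HbA1c and has since delivered. In both, HbA1c can change for reasons unrelated to quarantine, and an unadjusted paired test cannot separate that change from the effect of interest. A fall after treatment starts would hide a deterioration; a rise would mimic one. The affected values also enter the regression in 10.2 that uses previous HbA1c as a covariate.

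**Working it through.** **1. Which HbA1c does the pregnancy rule cover?** Sections 3, 8.3 and 11.2 use the term HbA1c measurement for the study fingerprick, and 8.3 and 11.2 say it is done once. In 8.4.1 itself, the COVID-19 criterion counts two weeks from the measurement, which fits only the study sample. The pregnancy criterion beside it most naturally means the same sample. The pregnancy exclusion in 4.3, read at enrolment, does not reach a pregnancy already ended.

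**2. How far back does the malignancy exclusion reach?** Section 8.3 places the study sample two months into quarantine. A 6-month exclusion then reaches about 6 − 2 = 4 months before quarantine. That is 4/6, about two thirds, of a 6-month look-back and 4/12, one third, of a 12-month one. The withdrawal rule is undated and speaks of HbA1c values in the plural, so it may cover the rest. Malignancy is therefore partly protected.

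**3. The plan's own figures.** From section 4.4: difference 4.0, SD 11, "For an alpha error of 0.05 and a power of 90%, the minimum sample needed is 159 patients per patient group". The two-sided formula for two independent groups gives

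n = 2 × (1.960 + 1.282)² × 11² / 4.0² ≈ 158.9, so 159.

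Invitations, with "estimated response rate of 35% and an estimated proportion of 20% of HbA1c missing measurements": 159 / (0.35 × 0.80) = 567.9, so 568. Both reproduce. The independent-groups formula does not match the planned paired test, but that is a separate matter and does not affect this point.

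**4. Size of the bias.** The documents give neither the share of affected pairs (f) nor their net unrelated change (s); both are assumed here.

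Bias in the mean change = f × s.

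For the false-positive rate, also assume no true quarantine effect, n = 159 and an SD of change of 11 in unaffected pairs. The SD is then √(11² + f(1 − f)s²), used in a two-sided 5% paired t-test.

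| Share f | Shift s (one direction) | Bias (mmol/mol) | Share of 4.0 | False-positive rate |
|---|---|---|---|---|
| 1% | 10 | 0.1 | 2.5% | 5.1% |
| 2% | 20 | 0.4 | 10% | 7.3% |
| 2% | 30 | 0.6 | 15% | 9.8% |
| 5% | 20 | 1.0 | 25% | 18.5% |
| 5% | 30 | 1.5 | 37.5% | 31.2% |

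Counted in patients, 3 of 159 gives 3 × 20/159 = 0.38 to 3 × 30/159 = 0.57. For scale, the standard error without contamination is 11/√159 = 0.87.

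**5. Cancellation.** If 2% fall by 20 and 1% rise by 20, the net bias is −0.4 + 0.2 = −0.2 mmol/mol. The table shows the one-directional case.

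**The case against.** Several points on the other side stand.

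- A reader might infer that the rules protect only the quarantine value. For malignancy that is not so, as step 2 shows.
- A reader might infer that a prior value taken during chemotherapy now finished is allowed. The chemotherapy and immunotherapy exclusion carries no dates. It is ambiguous for the prior value, which is different from permitting it.
- A reader might extend the point to values taken in hospital. The Protocol gives no reason for excluding admitted patients and nowhere links admission to HbA1c validity. An inpatient is not in self-quarantine at home, which explains the criterion equally well.
- A value at diagnosis becomes the baseline only if no later pre-quarantine value exists. The Summary describes tertiary care and section 4.4 often well regulated patients, so such cases may be few.
- A bias of 25% or more of the target needs about 5% of pairs, all shifted by at least 20 mmol/mol in the same direction. No figure in the document supports that.
- The Wilcoxon test, if used, limits the pull of a few extreme pairs.
- It is tempting to add that the type 1 versus type 2 comparison is distorted. Section 10 names a difference in HbA1c between types without saying whether values or changes are compared. If quarantine values are compared, the prior value does not enter.

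It could also be said that the choice of valid prior values belongs in a statistical analysis plan. That answers only part of the point: eligibility and the data to be collected are fixed in the Protocol, and an analysis plan cannot exclude on a date of diagnosis that was never retrieved.

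**Conclusion.** The point holds for two groups: patients whose last pre-quarantine HbA1c dates from a recent diagnosis, and women pregnant at that value and since delivered. Following the Protocol as written counts their change as an effect of quarantine. For malignancy the gap is partial, and for chemotherapy or immunotherapy the wording is unclear.

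The size is unknown. At 1% to 2% of pairs the bias is small against 4.0 mmol/mol; it becomes material at about 5% or more with large shifts in one direction. Without diagnosis dates the investigators could not show which case applies. Because the defect biases the primary estimate and is cheap to remove, it should be corrected, though it does not by itself undermine the study.

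**What to change.** - In 8.4.1 and 10.1, apply the pregnancy and malignancy criteria for HbA1c validity at the date of the prior value as well as the study value. State whether the chemotherapy and immunotherapy exclusion in 4.3 covers that date.
- If the last prior value fails, use the nearest earlier valid value within the look-back window; if there is none, leave the patient out of the paired analysis. This needs one window, so the 6 and 12 months in 8.3 and 3 must be reconciled first.
- Add date of diabetes diagnosis to 8.1.3 and retrieve it from the record. Leave out of the paired analysis patients whose prior value was taken within a prespecified time of diagnosis or, at the least, repeat the analysis without them as a prespecified sensitivity analysis. The Protocol offers no basis for a particular cut-off, so the investigators should choose and justify one before seeing the data.
- Keep all these patients in the questionnaire analyses.

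The cost is some wording, one more field, and a check of status at the prior date in a record already being consulted. A few pairs per type are lost: dropping 3 of 159 raises the standard error only from 11/√159 = 0.87 to 11/√156 = 0.88. Falling back to an earlier value sometimes lengthens the gap between the two measurements.
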